10.4 Exploratory Endpoints

Exploratory endpoints for this study include:

- To standardize and expand the quantity and quality of sociodemographic (e.g., racial/ethnic distribution, SES), HIV-related health [e.g., Antiretroviral Therapy (ART) medications, co-morbidities], and cancer diagnostic and treatment characteristics collected for PWH receiving care at domestic AMC sites.

- To describe cancer patient health-related QOL for PWH at domestic AMC sites using EORTC QLQ-C30 and SCNS-SF34.

Exploratory endpoints will be analyzed as described below:

1. The distribution of participant characteristics from [Table 2-A](#) will be summarized.
2. The frequency of planned cancer treatment regimens successfully initiated will be summarized.
3. PRO assessment scores from the EORTC QLQ-C30 and SCNS-SF34 will be summarized, both overall and at the ~12-week follow-up, according to participant characteristics and cancer groups. Overall change in PRO measures will be compared with paired tests and change according to groups will be compared using t-tests, ANOVA, or nonparametric tests. In an exploratory manner, PRO scores for PWH who are in remission will be analyzed separately to understand longer-term QOL issues that may inform future POSEC-led survivorship efforts.

10.5 Data and Safety Monitoring Board Review

Per the AMC's Data and Safety Monitoring Plan (DSMP; see [Appendix III](#)), DSMB reviews are only required for phase III randomized trials by NCI policy. This study will be monitored for safety and trial progress according to the procedures outlined in the DSMP only.

11.0 ROLE OF DATA MANAGEMENT AND DATA REPORTING

11.1 Study Oversight

This protocol is monitored at several levels, as described in this section. The Protocol Principal Investigator is responsible for monitoring the conduct and progress of the clinical trial, including the on-going review of accrual and patient-specific clinical and laboratory data. The Protocol Principal Investigator and statistician have access to the data at all times through the CTMS web-based reporting portal.

All Study Investigators at participating sites who register/enroll participants on a given protocol are responsible for timely submission of data via Medidata Rave. This includes timely review of data collected on the electronic CRFs submitted via Medidata Rave.

Permission to view and download this protocol and its supporting documents is restricted and is based on person and site roster assignment housed in the CTSU Regulatory Support System (RSS).

This study is supported by the NCI Cancer Trials Support Unit (CTSU).

All studies are also reviewed in accordance with the enrolling institution's data safety monitoring plan.

11.2 CRF Instructions

Access to the internet data entry system for this study, iMedidata Rave, and instructions for recording of study data on eCRFs will be provided by the AMC ODMC at www.AIDSCancer.org. Participating institutions are responsible for submitting data and/or data forms via iMedidata Rave in accordance with the AMC Data Entry Guide and specific form instructions, within the timelines specified by the AMC's Standards of Procedure for Site Performance Measures.

11.3 Data Quality

It is the responsibility of the AMC ODMC to assure the quality of data for the study (See [Appendix III](#), AMC Data and Safety Monitoring Plan). This role extends from protocol development to generation of the final study database.

11.4 Data Reporting

Medidata Rave is a clinical data management system being used for data collection for this trial/study. Access to the trial in Rave is controlled through the CTEP-IAM system and role assignments. To access Rave via iMedidata:

- Site staff will need to be registered with CTEP and have a valid and active CTEP-IAM account, and
- Assigned one of the following Rave roles on the relevant Lead Protocol Organization (LPO) or Participating Organization roster at the enrolling site: Rave CRA, Rave Read Only, Rave CRA (LabAdmin), Rave SLA, or Rave Investigator. Refer to <https://ctep.cancer.gov/investigatorResources/default.htm> for registration types and documentation required.
 - To hold Rave CRA or Rave CRA (Lab Admin) role, site staff must hold a minimum of an AP registration type,

- To hold Rave Investigator role, the individual must be registered as an NPIVR or IVR, and
- To hold Rave Read Only role, site staff must hold an Associates (A) registration type.

If the study has a DTL, individuals requiring write access to Rave must also be assigned the appropriate Rave tasks on the AMC DTL.

Upon initial site registration approval for the study in Regulatory Support System (RSS), all persons with Rave roles assigned on the appropriate roster will be sent a study invitation e-mail from iMedidata. To accept the invitation, site staff must log in to the Select Login (<https://login.imedidata.com/selectlogin>) using their CTEP-IAM username and password and click on the accept link in the upper right-corner of the iMedidata page. Site staff will not be able to access the study in Rave until all required Medidata and study specific trainings are completed. Trainings will be in the form of electronic learnings (eLearnings) and can be accessed by clicking on the link in the upper right pane of the iMedidata screen. If an eLearning is required and has not yet been taken, the link to the eLearning will appear under the study name in iMedidata instead of the Rave EDC link; once the successful completion of the eLearning has been recorded, access to the study in Rave will be granted, and a Rave EDC link will display under the study name.

Site staff that have not previously activated their iMedidata/Rave account at the time of initial site registration approval for the study in RSS will also receive a separate invitation from iMedidata to activate their account. Account activation instructions are located on the CTSU website in the Rave section under the Rave resource materials (Medidata Account Activation and Study Invitation Acceptance). Additional information on iMedidata/Rave is available on the CTSU members' website in the Data Management > Rave section at www.ctsu.org/RAVE/ or by contacting the CTSU Help Desk at [name] or by e-mail at [contact].

11.5 Data Monitoring

Required submission of patient demographic data for this study will be submitted automatically via OPEN.

12.0 ETHICAL AND REGULATORY CONSIDERATIONS

12.1 IRB Approval and Informed Consent

Records of all study review and approval documents must be kept on file by the Investigator and are subject to inspection during or after completion of the study. The IRB should receive notification of completion of the study and final report within 3 months of study completion and termination. The Investigator will maintain an accurate and complete record of all submissions made to the IRB, including a list of all reports and documents submitted.

To determine the types of cancer cases that present to the clinical sites, it is requested that all cancer patients presenting at these sites have a minimum set of de-identified data collected. This will be performed prior to formal consent and meets criteria for minimal risk data collection. Data collected on cancer patients presenting to the clinical site will include age, sex at birth, race/ethnicity, and type of cancer. Data collected during screening will be maintained separately from data on enrolled cases. No other data will be collected on patients who do not consent to participate in AMC-115.

Written informed consent will be obtained from the participant to collect identifiable data. The nature, significance and risks associated with the study must be explained to the participant. The informed consent will describe the purpose of the study, the procedures to be followed, the risks and benefits of participation, all risks of the investigational agent(s) and/or study participation as listed in the model informed consent form, and all other elements of informed consent as required by regulation. A copy of the consent form will be given to the participant to keep.

In addition, any institution(s) conducting research according to the guidelines of this protocol is required to adhere to local and national laws and regulations governing the confidentiality and disclosure of health information.

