3.1 Eligibility Criteria

_____ 3.1.1 Participant can understand and is willing to sign a written informed consent document.

_____ 3.1.2 HIV positive. Documentation of HIV-1 infection by means of any one of the following:

- Documentation of an HIV diagnosis in the medical record by a licensed health care provider;
- Documentation of receipt of antiretroviral therapy (ART) (i.e., at least two different medications that do not constitute a prescription for pre-exposure prophylaxis [PrEP]) by a licensed health care provider. Documentation may be a record of an ART prescription in the medical record, a written prescription in the name of the participant for ART, or pill bottles for ART with a label showing the participant's name;
- HIV-1 RNA detection by a licensed HIV-1 RNA assay demonstrating >1000 RNA copies/mL;
- Any licensed HIV screening antibody and/or HIV antibody/antigen combination assay confirmed by a second licensed HIV assay such as a HIV-1 Western blot confirmation or HIV rapid multispot antibody differentiation assay.

Note: The term "licensed" refers to a kit that has been certified or licensed by an oversight body within the participating country and validated internally (e.g., U.S. FDA).

WHO (World Health Organization) and CDC (Centers for Disease Control and Prevention) guidelines mandate that confirmation of the initial test result must use a test that is different from the one used for the initial assessment. A reactive initial

rapid test should be confirmed by either another type of rapid assay, or an E/CIA that is based on a different antigen preparation and/or different test principle (e.g., indirect versus competitive), a Western blot, or a plasma HIV-1 RNA viral load.

- _____ 3.1.3 Patient was diagnosed with or treated for cancer within the last 5 years. Participants will qualify under one of three categories:
- New, primary or recurrent diagnosis –Considering or currently receiving cancer treatment
 - Metastatic or locally advanced cancer – This includes cases for which there are no current definitive therapy options for cure (i.e., inoperable) but may be considered for non-standard / non-curative therapies.
 - Prior diagnosis (within 5 years), in remission – Not currently on cancer treatment other than ART or maintenance therapy.
- _____ 3.1.4 Age \geq 18 years.
- _____ 3.1.5 Participant presents to an AMC domestic clinical trial site for either clinical care or research.

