8.1 Screening

All PWH who present for care at participating AMC clinical trial sites with a histologically confirmed diagnosis of cancer (within the past 5 years) will be tracked on a screening list. Eligibility will be assessed for each patient on the list, and if they are determined eligible, they will be approached to participate in AMC-115.

To determine the types of cancer cases that present to the clinical sites, all participants presenting at these sites have a minimum set of de-identified data collected. This minimal risk data collection will only include the participant's age, sex at birth, race/ethnicity, and type of cancer and will be performed prior to formal consent. Data collected during screening will be maintained separately from data on enrolled cases. This data will be compared to the total number of enrolled participants at each site to estimate the proportion of participants who consent to participate in this trial.

The protocol chair has established a set of IT logic codes that can be applied to electronic health record (EHR) systems to automate screening for "HIV status" among cancer patients. This is critical as it (1) makes the ascertainment of PWH and cancer uniform across participating domestic AMC sites and (2) reduces physician and study coordinator burden by leveraging the electronic medical record and automating the search. To ensure that this IT-based approach can be implemented across domestic AMC sites, the feasibility survey included a question specifically about the ability of sites to search their electronic medical record systems for HIV-specific disease codes.

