10.3 Analysis of Secondary Endpoint and Analysis

The secondary endpoint is the proportion of participants eligible for AMC trials who are successfully enrolled.

For this calculation, the denominator will be computed based on PWH deemed eligible at each site, based only on AMC trials open at that respective site.

For participants with active disease, each participant's data will be evaluated to determine whether they meet minimal eligibility criteria for an AMC clinical trial open at

their respective domestic site, defined as meeting the following minimum eligibility criteria per the protocol:

- a. Cancer diagnosis including stage and histology
- b. Age range specified in the protocol for which the patient is being screened
- c. Indication for the study intervention (e.g., symptom, toxicity)

These data will be compared to the actual number of participants enrolled onto AMC trials open at each site to estimate the proportion of trial-eligible participants who enroll. For participants with a history of malignancy diagnosed within the past 5 years / cancer currently in remission, each patient's performance status and HIV metrics (CD4+ T-cell count and HIV viral load) will be evaluated to determine whether they meet general levels that are consistent with eligibility criteria for prior AMC clinical trials. To characterize participants who are eligible but not enrolled onto AMC trials, participant characteristics for eligible participants will be compared according to successful enrollment versus not using two-sample tests for continuous and categorical data (e.g., t-test, Wilcoxon rank sum test, chi-square test). Characteristics will include demographic features, clinical/cancer features, and optional QOL responses.

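### The trial-enrolment proportion in 10.3 can be worked out only among AMC-115 consenters, but it is not labelled that way and its numerator may count other people

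*Combined protocol and SAP*

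**What the plan says.** Section 10.3 defines the endpoint: "The secondary endpoint is the proportion of participants eligible for AMC trials who are successfully enrolled". It adds that "the denominator will be computed based on PWH deemed eligible at each site", counting only AMC trials open there. For people with active disease, the minimum criteria are "Cancer diagnosis including stage and histology", the age range of the trial in question, and an indication for its intervention. For people in remission it looks at performance status, CD4+ count and HIV viral load. The other side of the ratio is described thus: "These data will be compared to the actual number of participants enrolled onto AMC trials open at each site".

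Sections 8.1 and 12.1 fix what is known before consent: cancer type, age, race/ethnicity and sex at birth, de-identified and stored apart from the records of enrolled cases. Section 12.1 closes the matter for everyone else: "No other data will be collected on patients who do not consent to participate in AMC-115".

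Section 8.1 gives the screening list one analytic use: "This data will be compared to the total number of enrolled participants at each site to estimate the proportion of participants who consent" to AMC-115. Section 10.3 does not refer to the list and has no weighting, bound or sensitivity analysis for non-consent.

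**The concern.** The information that decides trial eligibility is collected only after consent to AMC-115. A person who does not consent cannot be classed as eligible and enrolled, or as eligible and not enrolled. The endpoint, and the comparison of enrolled with non-enrolled people built on it, are therefore conditional on AMC-115 consent. Section 10.3 does not say so, and its wording suggests a site-wide rate.

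Two separate problems follow. First, the enrolment count may cover everyone on AMC trials at the site while the denominator covers consenters only. That inflates the ratio even if consenters and others are equally willing to join trials. Second, even with matched counts, consenters may differ from others in willingness. An upward error is plausible: someone who declines a low-burden study may also decline a trial, and criterion 3.1.5 admits people who come for research ("Participant presents to an AMC domestic clinical trial site for either clinical care or research").

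Section 2.1 stresses learning about people who are eligible for a trial but opt out, and 10.3 wants the results to inform efforts to raise participation. A consenters-only figure read as the site's participation rate could misdirect that work.

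**Working it through.** **No stated figure to reproduce.** The plan gives no expected value, precision or consent rate for this endpoint. Table 10-A concerns the primary objective. Its eight percentage intervals reproduce to 0.1 point with p ± [1.96·√(p(1−p)/n) + 1/(2n)]; for example, p = 12.5% and n = 720 give 10.0% to 15.0%. It is not in question here.

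**Where each item is available**

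| Needed for 10.3 | AMC-115 consenters | Everyone else on the list |
|---|---|---|
| Age, cancer type | yes | yes |
| Stage, histology, indication | yes | no |
| Performance status, CD4+, viral load | yes | no |
| Enrolment in a trial | yes (Table 2-A) | no |

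**Inputs, all assumed because the documents give none:** c = share of trial-eligible people with HIV who consent to AMC-115 (75% or 50%); p = trial-enrolment proportion among eligible consenters (20%); RR = enrolment rate in non-consenters relative to consenters.

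**Step 1: unmatched counts, equal willingness (RR = 1).** Take 100 eligible people at a site, of whom 20 enrol.
- c = 75%: the matched ratio is 15/75 = 20%. With all site enrolments on top it is 20/75 = 26.7%, which is 1/0.75 = 1.33 times too high.
- c = 50%: matched 10/50 = 20%; unmatched 20/50 = 40%, which is 1/0.50 = 2.00 times too high.

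The inflation is 1/c if every outside enrolment is counted, and less if only some are.

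**Step 2: matched counts, unequal willingness.** The rate in all eligible people is P = p·[c + (1−c)·RR]. The consenter figure therefore differs from P by the factor 1/[c + (1−c)·RR], which does not depend on p.

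| RR | c = 75% | c = 50% |
|---|---|---|
| 0 | 1.33 | 2.00 |
| 0.5 | 1.14 | 1.33 |
| 1 | 1.00 | 1.00 |
| 1.25 | 0.94 | 0.89 |

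For RR = 0.5: 1/(0.75 + 0.25 × 0.5) = 1/0.875 = 1.14, and 1/(0.50 + 0.50 × 0.5) = 1/0.75 = 1.33. Below RR = 1 the consenter figure is too high; above it, too low.

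**Step 3: limits without assuming RR.** If no non-consenter enrols, P = c·p. If all do, P = c·p + (1−c). With p = 20%:
- c = 75%: 0.15 to 0.15 + 0.25, or 15% to 40%.
- c = 50%: 0.10 to 0.10 + 0.50, or 10% to 60%.

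The lower limit can be estimated from planned data if eligibility is assumed equally common in consenters and others, so that the consent proportion from the screening list can stand in for c.

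**The case against.** The best defence is that 10.3 already speaks of participants and of each participant's data, and that Table 2-A records trial enrolment for everyone who consents. On that reading the counts match, and 8.1 will report the consent proportion in any case. This has weight: no stated figure is wrong, and people who join AMC-115 but turn down a trial are captured and compared. A reader might infer that the study misses those who opt out of trials; it misses only those who also stay out of AMC-115. But the wording does not settle the matter. Section 8.1 uses the word participants for people not yet consented, and 10.3 describes its denominator by site, not by AMC-115 membership.

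Three stronger readings are tempting and not supported:

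- *The endpoint overstates participation.* With matched counts this requires RR below 1. No section gives or tests RR; at RR = 1 there is no error, and above 1 the sign reverses.
- *Consent will be about 31%, so the inflation is about threefold.* This takes 720 over 763 × 3 = 2,289, or 31.5%, and 1/0.315 = 3.2. But 720 is the accrual maximum, and 2,289 assumes that all 16 surveyed sites are open for three years with no person recurring. The quotient is not a consent rate, and it mixes people not approached with people who refused.
- *AMC-trial registrations divided by the screening list give a lower bound.* Registrants need not be on a list limited to histologically confirmed cancer in people presenting for care. Overlap cannot be checked in de-identified records, and the list items do not separate active disease from remission.

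**Conclusion.** The concern holds in limited form. The secondary endpoint is conditional on AMC-115 consent without saying so, and its numerator is not tied to the people in its denominator. If outside enrolments are counted, the ratio is inflated by up to 1/c: 1.33 times at c = 75% and 2.00 times at c = 50%. With matched counts, the departure from the site-wide rate depends on an unknown RR: 1.14 or 1.33 times too high at RR = 0.5, nil at RR = 1, and too low above that. All values of c, p and RR are illustrations. An upward error is plausible but not established, so the consenter figure should not be treated as an upper bound. Data already planned can qualify the result, which makes this a cheap improvement; nothing in the plan's own figures needs correcting.

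**What to change.** Amend 10.3 as follows.

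1. Take numerator and denominator from the same AMC-115 participants, and label the result *among AMC-115 participants*.
2. Beside it, report the AMC-115 consent proportion by site, age, sex at birth, race/ethnicity and cancer type, from the 8.1 screening list.
3. Add sensitivity analyses. Weight the consenters to the screening-list margins; this corrects only for the listed items. Report the worst case c·p, stating that it assumes no non-consenter enrols and equal eligibility in both groups. Show results for several assumed relative rates, both below and above 1.
4. Use site counts of AMC-trial registrations only as a descriptive comparison, not as a bound.

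Nothing further is collected on non-consenters. The costs are some extra analysis, a reported figure that may be wider or less favourable, and a protocol amendment, which under 12.2 needs CTEP and CIRB approval.

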12.2 Changes to the Protocol

Any change or addition to this protocol requires a written protocol amendment that must be approved by CTEP and the Investigator before implementation. All amendments require approval by the CIRB.

12.3 Women and Minorities

This study is being conducted by the NCI-sponsored AMC. As part of their contractual obligations, each participating site within the AMC and the AMC as a whole is required to assure that the participation of women and minority participants reflects the percentage representation of these populations in their geographic region and, for the AMC, PWH in the United States as a whole. As such, it is expected that the representation of participants on this trial will reflect the constitution of the respective populations see [Table 12-A](#) for accrual targets.

Table 12-A: Accrual targets

DOMESTIC PLANNED SCREENING ENROLLMENT REPORT					
Racial Categories	Ethnic Categories				Total
	Not Hispanic or Latino		Hispanic or Latino		
	Female	Male	Female	Male	
American Indian/ Alaska Native	1	3	10	23	37
Asian	3	10	0	0	13
Native Hawaiian or Other Pacific Islander	1	2	0	0	3
Black or African American	98	230	10	23	361
White	38	88	30	70	226
More Than One Race	10	20	15	35	80
Total	151	353	65	151	720

